## 7.5 SERIOUS ADVERSE EVENTS AND DEATHS

Treatment-Emergent Serious adverse events (SAEs) will be summarized by system organ class and preferred term. The number and percentage of the subjects who experienced at least one SAE will be included.

Tabular summaries of the following SAEs will be provided:

- All SAEs regardless of the relationship to study drug
- SAEs related to study drug
- SAEs related to injection procedure
- Ocular SAEs (study eye) regardless of the relationship to study drug
- Ocular SAEs (study eye) related to study drug
- Ocular SAEs (study eye) related to injection procedure

In addition, separate listings will be created for deaths and all SAEs. List for SAEs will include the subject identifier, age, sex, verbatim term, preferred term, eye (N/A/OD/OS/OU), serious (yes/no), date of onset, relative study day of onset, duration of the event (or continuing), severity (mild/moderate/severe), causality (relationship to study drug/injection procedure), action taken (study drug permanently discontinued: yes/no), treatment (yes/no), and outcome (resolved/unresolved/fatal).

## 7.6 VITAL SIGNS

Descriptive statistics at each time point up through and including the Month 6 visit will be used to display the changes from Baseline for pulse, respiratory rate, and blood pressure (systolic and diastolic). Mean change of pulse, respiratory rate, and blood pressure (systolic and diastolic) from Baseline to the last measurement will be provided.

## 7.7 OPHTHALMIC VARIABLES

**Ophthalmic Examination.** The following ophthalmic examination variables will be analysed by shift table from Baseline to the pre-injection examination on Month 6 and from Baseline to the last visit (pre-injection) available (normal/abnormal, unless otherwise specified below):

- Examination of the motility
- Inspection of the lids/lacrimal/lashes
- Examination of the conjunctiva/sclera
- Inspection of the cornea
- Examination of the iris
- Examination of the pupils
- Inspection of the lens status (aphakic, pseudo-phakic, phakic; if phakic, nuclear/PSC/cortical 0, 1, 2, 3, 4), including a listing of subjects with a change in lens status for study eye and (separately) for fellow eye
- Examination of the posterior vitreous detachment
- Inspection of the optic nerve
- Inspection of the macula
- Examination of the retinal vessels

The following ophthalmic examination variables will be analysed by shift table from Baseline through Month 6 and for the last visit available, on a monthly basis (normal/abnormal, unless otherwise specified below), and from pre-injection to post-injection at each monthly injection

- Examination of the anterior chamber activity: Cells (0, trace, 1+, 2+, 3+, 4+)
- Inspection of vitreous haze (0, 1+, 2+, 3+, 4+)
- Examination of vitreous haemorrhage
- Examination of peripheral retina

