4.5 Clinical Data

4.5.1 Study OPH2000

In a phase 1 ascending dose and parallel group clinical trial the safety, tolerability, and pharmacokinetic profile of multiple intravitreal injections of Zimura™ in combination with Lucentis® 0.5 mg was evaluated in subjects with NVAMD (OPH 2000).

Zimura™ was well-tolerated and no particular safety concerns were identified. No significant evidence of intraocular inflammation, retinal vasculitis, or choroidal vasculopathy was evident. One patient was noted to develop a mild cataract, which was considered to be related to study drug by the investigator; despite this event, the visual acuity improved in this patient during the study.

Visual acuity (VA) assessments were primarily safety assessments to detect any decrease in vision associated with the intravitreal injections. There were no safety issues identified through measurement of VA. Assessment of VA was focused on the treatment-naïve (TN) patient subgroup of 43 patients who had received 6 injections at doses of 0.3 mg, 1 mg or 2 mg. There was a trend towards a mean increase in VA (number of ETDRS letters) from Baseline at all time points for patients in the 0.3, 1 and 2 mg dose groups in the TN subgroup who received 6 injections. At Week 24, there was an improvement in mean VA from Baseline of 13.6 ETDRS letters for the 0.3 mg dose group, 11.7 ETDRS letters for the 1 mg dose group and 15.3 ETDRS letters for the 2 mg dose group.

Fifty-one percent (51%) of patients in the TN subgroup (n=43 patients) gained ≥ 15 ETDRS letters at Week 24. This included 6 patients (46%) in the 0.3 mg dose group, 7 patients (47%) in the 1 mg dose group, and 9 patients (60%) in the 2 mg dose group gaining ≥ 15 ETDRS letters of VA.

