4.5.2 Study OPH2001

A separate phase 1 study was also performed in subjects diagnosed with geographic atrophy (GA). In this study, a total of 47 subjects were enrolled, in the 0.3 mg dose arm (n=24) and 1 mg dose arm (n=23). Subjects received treatment with 3 initial intravitreal injections of Zimura™ 0.3 mg/eye or 1 mg/eye, administered at Day 0, Week 4 and Week 8 with a follow up visit at Week 16. Subjects received 2 subsequent injections at Week 24 and Week 36 followed by a final follow up visit at Week 48. Standard safety assessments were performed for ophthalmic variables that included VA, IOP, ophthalmic examination, fundus autofluorescence (FAF), Fluorescein Angiography (FA), and optical coherence tomography (SD-OCT) together with AEs, vital signs and laboratory variables.

Zimura™ was well tolerated and there were no AEs considered to be related to Zimura™. Fifteen subjects (32%) had AEs, predominantly Eye Disorder AEs in the study eye, assessed to be related to the injection procedure. The most frequently reported AEs were conjunctival hemorrhage (4 subjects, 9%), corneal edema (4 subjects, 9%), and dry eye (3 subjects, 6%). No other study eye AEs were reported by more than 2 subjects. The majority of AEs were mild or moderate in severity. There were 2 subjects with AEs of severe intensity: gastrointestinal inflammation and nasopharyngitis.

Five subjects experienced serious adverse events (SAEs), namely device failure, pelvic fracture, angina pectoris, chest pain and gastrointestinal inflammation, but none were related to the study drugs or injection procedure. There were no discontinuations due to AEs.

Vital signs and laboratory assessments did not show any particular clinically significant patterns or changes. Study eye ophthalmic examinations did not indicate any unexpected clinical findings. There were some transient findings post-injection (conjunctiva/sclera and cornea) that resolved prior to the next injection. Vitreous haze was also reported for a few subjects. Intraocular pressure (IOP) showed a small mean increase following injections but no indication of any cumulative increases.

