7.3 Ophthalmologic Examination

The following examinations will be performed at all time-points specified in Sections 10.2 – 10.5 “Trial Assessments”.

- Inspection of the eyelids
- Examination of the extra-ocular muscle movement
- Inspection of the cornea
- Examination of the anterior chamber for inflammation (Appendix 17.1)

- Examination of the pupils
- Examination of the iris
- Inspection of the lens
- Inspection of the vitreous body (Appendix 17.2)
- Inspection of the retina and optic disc

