10.2.2 Day 1 (D0 Visit)

Pre-injection

- Protocol refraction and visual acuity (4 meters) using ETDRS chart (SE)
- Goldmann applanation tonometry and Ophthalmologic Examination (SE)

Injection

- Lucentis[®] 0.5 mg/eye

Post Injection

- Indirect Ophthalmoscopy (SE) – 1 to 2 minutes after the injection to assure that the optic nerve is perfused.
- Ophthalmologic exam/Tonometry (SE) – At least 30 minutes after the injection a full ophthalmologic exam must be performed and IOP must be < 30 mmHg before the subject leaves the clinic.

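### SAP 7.7 plans no by-cohort summary of post-injection conjunctiva/sclera and cornea findings, the two structures in which an earlier Zimura study saw transient changes

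*SAP*

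**What the plan says.** SAP 7.7 (Ophthalmic Variables) divides the examination into two lists.

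- **First list** (eleven variables: motility, lids/lacrimal/lashes, conjunctiva/sclera, cornea, iris, pupils, lens status, posterior vitreous detachment, optic nerve, macula, retinal vessels). These get a "shift table from Baseline to the pre-injection examination on Month 6 and from Baseline to the last visit (pre-injection) available" and nothing else.
- **Second list** (four variables: anterior chamber cells, vitreous haze, vitreous haemorrhage, peripheral retina). These get monthly shifts "and from pre-injection to post-injection at each monthly injection".

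Protocol 4.5.2 says of OPH2001: "There were some transient findings post-injection (conjunctiva/sclera and cornea) that resolved prior to the next injection".

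Post-injection examination is mandatory. At single-injection visits the rule reads "At least 30 minutes after the injection a full ophthalmologic exam must be performed" (for example Protocol 10.2.2). Where two injections fall on one day, the same examination follows the second.

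**The concern.** Safety is the trial's only objective, and the ophthalmic examination is a named safety endpoint (Protocol 5.2, SAP 2.1.1). The two structures with a reported history of short-lived post-injection findings sit in the list that excludes post-injection examinations. They are read before injection or at Month 6, about a month after the last scheduled dosing visit. By the protocol's own account, that is after such findings have gone.

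The trial studies a 4 mg dose and biweekly dosing (Protocol 4.6), and SAP 3.3.1 presents results by cohort. A by-cohort count of transient surface findings is a natural descriptive output for that purpose. The SAP already accepts the principle, because it tabulates post-injection change for four other examination variables and for IOP.

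**Working it through.** **1. The documents' own figures.** OPH2001 enrolled 47 subjects. Conjunctival hemorrhage and corneal edema were each reported as AEs in 4: 4/47 = 8.5%, stated as 9%. Dry eye: 3/47 = 6.4%, stated as 6%. Subjects with AEs related to the injection procedure: 15/47 = 31.9%, stated as 32%. All reproduce.

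**2. Planned post-injection examinations.** Injection visits per subject, from the schedules in Protocol section 3:

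- Cohort 1: 6 months × 2 visits (D0, D2) = 12
- Cohort 2: 6 × 1 = 6
- Cohort 3: 3 × 2 (D0, D14) + 3 × 1 = 9
- Cohort 4: 3 × 2 (D0, D14) + 3 × 2 (D0, D2) = 12

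With cohort sizes 10, 10, 20 and 20: 10×12 + 10×6 + 20×9 + 20×12 = 120 + 60 + 180 + 240 = **600** end-of-visit examinations. Each subject also has 6 days with two injections, so 60 × 6 = 360 further checks fall between injections. That makes 600 + 360 = 960 injections. This assumes full enrolment and no missed visits.

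**3. How many enter the shift tables for conjunctiva/sclera and cornea.** None, because both tables use examinations described as pre-injection. Month 6 itself has no injection in any cohort (Protocol section 3; 10.2.15, 10.3.8, 10.4.11, 10.5.14), so the wording in the SAP describes an examination that does not exist as such.

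**4. Where a finding would be reported.**

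- Persists to Month 6 or the last visit: SAP 7.7 shift tables.
- Transient and reported as an AE: the ocular TEAE tables in SAP 7.4, including those for injection-procedure-related events in the study eye.
- Transient and meeting none of the criteria for objective findings in Protocol 12.1: by-subject listings only (SAP 3.3.1).
- Exception: if a subject's last pre-injection examination is a D2 visit (Cohort 1, or Cohort 4 maintenance), it falls two days after an injection and might catch a transient finding.

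The gap is the third route.

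**5. An indication of frequency, not of the gap.** Assume the OPH2001 rate of 4/47 per subject applied here. The chance of at least one affected subject is 1 − (43/47)^n: 59% for n = 10, 83% for n = 20, 99.5% for n = 60. The expected number among 60 is 60 × 4/47 = 5.1. The 4/47 counts are reported AEs, so the calculation shows only that post-injection surface events are likely to occur in these cohorts. It says nothing about how many findings would go unreported as AEs. Protocol 4.5.2 says only that there were some transient findings. The rate is also uncertain here: OPH2001 planned 3 + 2 = 5 injections per subject at 0.3 or 1 mg in geographic atrophy, whereas this trial plans 960/60 = 16 per subject on average, at other doses and in another disease.

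**The case against.** Several stronger readings are tempting, and the documents do not support them.

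- **That about 5 of 60 subjects with corneal edema, and as many with conjunctival hemorrhage, would be hidden.** In OPH2001 these were reported AEs. Reported the same way here, they would appear in several SAP 7.4 tables.
- **That the tables would look clean whatever happened.** Persistent findings would show at Month 6 or the last visit. Cells, haze, haemorrhage and peripheral retina are tabulated pre- to post-injection, and IOP is summarised after each injection.
- **That data are lost.** SAP 3.3.1 lists all CRF data by subject, and in a descriptive trial of 60 subjects listings are usable.
- **That the precedent extends to optic nerve, retinal vessels or iris.** Protocol 4.5.2 names only conjunctiva/sclera and cornea. The OPH2000 summary says "No significant evidence of intraocular inflammation, retinal vasculitis, or choroidal vasculopathy was evident". For these other structures the omission of post-injection tables is real but rests on no reported earlier transient finding. Imaging may also cover the posterior segment, but the list of endpoints in SAP 7.3 is redacted, so nothing can be concluded from it.

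The strongest remaining case is that what escapes is mainly asymptomatic, untreated and self-resolving, that Protocol 12.1 also lets the investigator or sponsor call any finding an AE, and that Protocol 11.4.4 promised no examination shift tables. All of that stands, and it narrows the point. It does not explain why the two structures with a reported precedent are the ones left out of the pre- to post-injection tables when the examinations are already required.

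One further caveat stands. The examination list in Protocol 7.3 names the cornea but not conjunctiva/sclera. The latter appears as a variable in SAP 5 and 7.7, and the CRF is not available to confirm that it is recorded after injection.

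**Conclusion.** The point holds as a gap in summary tables, not as a loss of data or a concealment of adverse events. For conjunctiva/sclera and cornea, none of the 600 planned end-of-visit post-injection examinations contributes to the SAP 7.7 shift tables. Transient findings there that are not reported as AEs would have no counts by cohort. How many such findings there would be cannot be estimated from the documents.

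The conclusion assumes that the schedule is completed as planned, that conjunctiva/sclera is recorded at post-injection examinations, and that the transient course described for OPH2001 applies at the doses and frequencies used here. Separately, the reference to a pre-injection examination at Month 6 is a wording error, because no injection is scheduled then.

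**What to change.** In SAP 7.7:

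1. Add conjunctiva/sclera and cornea to the second list, tabulated monthly and from pre- to post-injection. State that this applies at each injection visit, so that D2 and D14 visits are plainly included.
2. For the first-list variables, add one shift from Baseline to the worst post-baseline examination, with post-injection examinations included. This also covers optic nerve and retinal vessels without claiming a precedent for them.
3. Refer simply to the Month 6 examination and drop the description of it as pre-injection.
4. Confirm that the CRF records conjunctiva/sclera after injection.

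The cost is SAP text, table programming and a slightly longer table package. No site procedure changes. The added tables would describe the combined regimen and injection procedure: with no Lucentis-only arm, they cannot attribute a finding to Zimura alone.

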4 INTRODUCTION

4.1 Age-Related Macular Degeneration (AMD)

Age-related macular degeneration is a disease characterized by progressive degenerative abnormalities in the macula of the eye, a small area in the central portion of the retina. It is characteristically a disease of individuals > 50 years of age and is the leading cause of visual loss in developed countries (Van Newkirk et al., 2000). In the United States, it is estimated that approximately 6% of individuals 65 - 74 years of age and 20% of those older than 75 years of age are affected with AMD (Leibowitz et al., 1980). Because of the increasing life expectancy in developed and developing countries, the elderly sector of the general population is expected to rise at a greater rate in the coming decades (Ortma et al., 2014). While 1 of 8 Americans was aged 65 or older in 2012, it is expected that 1 of 5 will fall into this category in 2030 (US Census Bureau, 2012). Using U.S. Census Bureau projections, the number of Americans over 65 years of age will double to 80 million by the middle of this century (US Census Bureau, 2012). In the absence of adequate prevention or treatment measures, the number of cases of AMD with visual loss is expected to grow accordingly.

Age-related macular degeneration is classified into one of two general subgroups: the non-neovascular (non-exudative or dry) form of the disease and the neovascular (exudative or wet) form of the disease. The non-neovascular form of AMD is more prevalent, accounting for approximately 90% of all AMD cases, and is often characterized by a slow degeneration of the macula resulting in atrophy of the central retina with gradual vision loss over a period of years. By contrast, NVAMD, although less prevalent, commonly causes sudden, often substantial, loss of central vision and is responsible for most cases of severe loss of visual acuity in this disease (Vingerling, 1995). This type of AMD results when abnormal blood vessels (neovascularization) proliferate under and/or within the retina. These blood vessels leak blood and fluid into and under the retina, which results in rapid vision loss. The end stage of the disease features scarring with irreversible destruction of the central retina.

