10 TRIAL CONDUCT

10.1 Subject Enrollment

Before recruitment of subjects into the trial, written Institutional Review Board (IRB) or Ethics Committee (EC) approval of the protocol and informed consent must be obtained.

Subjects who meet the eligibility criteria and have provided written informed consent will be enrolled in the trial. If any inclusion or exclusion criteria are not met, treatment with trial drug should not commence without prior written approval from Ophthotech Corp. or its designee.

Written informed consent must be obtained before any of the Screening procedures listed below are performed. However, if a routine office procedure (e.g. FA, OCT) is performed to diagnose NVAMD independent of this clinical trial, and subsequently the subject provides informed consent for this study, these procedures performed prior to informed consent may be used as screening assessments for this study, provided the 14-day period of screening evaluations is respected and provided the assessments are acceptable to the standards of the study. An explanation of the trial and discussion of the possible risks and discomforts will be given by the investigator.

For the Screening visit only, assessments can be broken into 2 days if necessary. For all other visits, all assessments indicated must be performed on the same day.

The RC will determine eligibility of all subjects prior to enrollment. Only those subjects who fulfill all eligibility criteria will be entered into the trial.

The following assessments will be performed during the study.

10.2 Trial Assessments – Cohort 1

The following dosing days apply to subjects in Cohort 1.

D0	D0 = The first day of dosing at each monthly timepoint.
D2	D2 = The second day of dosing, 2 days after D0.

The following evaluations, as outlined in the Study Assessments Chart (see Section 3), will be performed on the days specified below:

Note:

- **Concomitant Medications should be assessed at every study visit.**
- **Adverse events (AEs) should be assessed starting at Day 1 after the first dose of trial drug.**

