## 2 STUDY DESIGN AND OBJECTIVES

### 2.1 STUDY OBJECTIVE

The objective of this study is to assess the safety of intravitreal Zimura™ administered in combination with Lucentis® 0.5 mg in treatment naïve subjects with neovascular age related macular degeneration (NVAMD)

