## 7.9 ECG

ECG results will be tabulated at Baseline as “normal”, “abnormal, not clinically significant” or “abnormal, clinically significant”. At follow-up visits, ECG results will be tabulated as “no change from Baseline”, “NOT clinically significant change from Baseline” or “clinically significant change from Baseline”. A by-patient listing will be provided for ECGs which are deemed clinically significant.

[figure not shown]

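### The normal/abnormal macula shift in SAP 7.7 can show almost no worsening in study eyes, because NVAMD eyes should enter as abnormal

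*SAP*

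**What the plan says.** SAP 7.7 lists examination items to be analysed by shift table from Baseline to Month 6, and also "from Baseline to the last visit (pre-injection) available (normal/abnormal, unless otherwise specified below"). The entry "Inspection of the macula" is on that list with no scale of its own, so the two-level default applies.

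Other items in the same section are graded. The lens entry reads "Inspection of the lens status (aphakic, pseudo-phakic, phakic; if phakic, nuclear/PSC/cortical 0, 1, 2, 3, 4") and also has a listing of subjects whose status changes, separately for study and fellow eye. Anterior chamber cells and vitreous haze have ordinal grades. SAP 7.7 does not say which eye the macula table covers.

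SAP 2.1 defines the population as "treatment naïve subjects with neovascular age related macular degeneration (NVAMD"). Protocol 4.1 states: "Age-related macular degeneration is a disease characterized by progressive degenerative abnormalities in the macula of the eye". Protocol 10.1 adds an independent check: "The RC will determine eligibility of all subjects prior to enrollment".

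**The concern.** A two-level shift table shows harm only when a subject starts in the better level. The macula is the site of the disease under study, so study eyes should start in the worse level. A new finding in such an eye then leaves no trace in the table.

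Protocol 10.2.1.1, repeated for the other cohorts, gives examples of what could be lost. It treats a large subretinal bleed, an RPE tear or a pigment epithelial detachment, seen on clinical examination between Screening and Day 1, as a significant anatomical change that bars entry. The same finding arising on treatment in an already abnormal macula would be tabulated as no shift.

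Safety is the only objective, and the ophthalmologic examination is a named safety endpoint (SAP 2.1 and 2.1.1). At stake is whether this summary can compare macular deterioration across the four cohorts.

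**Working it through.** The plan states no figure for this point. There is no hypothesis test, power or sample size calculation behind it (SAP 2.3), so the check is a logical one on the shift table.

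**Inputs**
- Scale for the macula: normal/abnormal (SAP 7.7).
- Entry condition: NVAMD (SAP 2.1), in a disease that the protocol describes as abnormality of the macula (Protocol 4.1).
- Baseline lesion in the study eye: CNV location is extrafoveal, juxtafoveal or subfoveal, with no category for absent CNV (SAP 5).
- Planned subjects by cohort: 10, 10, 20 and 20 (SAP 2.2), so 10 + 10 + 20 + 20 = 60 study eyes.
- No passage in the text provided redefines abnormal to mean abnormal beyond the NVAMD itself.

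**What each cell can hold**

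| Baseline | Follow-up | Meaning |
|---|---|---|
| Normal | Normal | No change |
| Normal | Abnormal | Worsening (the only cell that shows it) |
| Abnormal | Abnormal | Stable, partly improved or worsened, not separated |
| Abnormal | Normal | Improvement |

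**Ceiling on visible worsening**

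The largest possible count in the normal-to-abnormal cell is the number of study eyes recorded normal at Baseline. Call the proportion so recorded p; the ceiling is then 60 × p. The documents give no value for p, so a range is shown:
- p = 0: 60 × 0 = 0 eyes (0 of 10, 0 of 10, 0 of 20 and 0 of 20 by cohort).
- p = 5%: 60 × 0.05 = 3 eyes, leaving 57 that cannot register a worsening.
- p = 10%: 60 × 0.10 = 6 eyes, leaving 54 that cannot.

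These ceilings hold whatever the true rate of macular worsening.

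**Fellow eye**

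The Baseline ophthalmic examination is summarised for both eyes (SAP 5). Both eyes are examined at Screening, Month 3, Month 6 and Early Withdrawal (SAP 3.1). A fellow eye with a normal macula at Baseline can therefore enter the normal-to-abnormal cell, so the restriction applies to study-eye rows only.

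**How the SAP treats other measures that may be abnormal at entry**
- SAP 7.8 gives subjects with abnormal Baseline laboratory results their own table, with secondary criteria relative to Baseline.
- SAP 7.9 tabulates follow-up ECGs by change and not by status, including a category for "clinically significant change from Baseline".
- The macula has neither arrangement.

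**The case against.** The strongest objection is that this is one row of one table, and that more sensitive measures of the macula are already planned:
- SAP 7.2 reports acuity by visit and cohort, with percentages of subjects losing letters.
- SAP 7.3 is devoted to OCT and FA, and SAP 5 shows that lesion area, CNV area and central subfield thickness are measured at Baseline.
- SAP 7.4 and 7.5 tabulate study-eye adverse events and serious adverse events.
- SAP 3.3.1 provides listings of all CRF data.
- The dose-limiting toxicity rules in Protocol 9.2.3 use acuity and SD-OCT, not this table.

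This stands, and it rules out the inference that the trial cannot detect macular harm. The other routes do not repair the table, however. Protocol 12.1 keeps insufficient response out of adverse event reporting, acuity is a functional measure, and listings give no summary by cohort. The SAP 7.3 endpoint list is redacted, so it cannot be counted for or against the plan.

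A reader might also infer that the table will be taken as evidence of no harm. The documents do not support that. The analysis is descriptive, no stated decision rests on this row, and a row almost entirely abnormal-to-abnormal is visibly uninformative.

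Finally, the ECG parallel is only a parallel. SAP 7.9 gives no reason for its format, and change categories need a judgement that the CRF may not capture for the macula. That bears on the cost of the fix, not on the limitation itself.

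**Conclusion.** The point holds for the study eye, as a low-cost improvement that should be made. As specified, the study-eye macula rows can show improvement or no shift, but almost no worsening. No error rate, sample size or dosing decision is affected.

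The figure of 0 of 60 should be read as an inference and not as a documented count. It assumes that examiners record an NVAMD macula as abnormal. That is well supported by the entry diagnosis, the protocol's description of the disease and the Reading Committee check, but the ophthalmic inclusion criteria and the CRF are not visible. If up to 10% of study eyes were recorded normal, at least 54 of 60 would still be unable to register a worsening.

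It would go too far to say that the table cannot show any macular worsening. SAP 7.7 does not confine it to the study eye, and fellow-eye rows can show it.

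**What to change.** In SAP 7.7:
- State which eye each shift table covers.
- For the study-eye macula, replace or supplement the binary shift with change from Baseline, in three categories (improved, unchanged, new or worsened finding), by cohort.
- Add a by-subject listing of new or worsened study-eye macular findings, like the listing already planned for lens status.
- Derive these from examination findings already recorded. Where the CRF does not capture change, either code the recorded findings under a rule set before database lock or add one CRF item.
- Add counts of named findings from Reading Committee images only if the redacted list in SAP 7.3 does not already contain them.

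Normal/abnormal can remain for the fellow eye. The cost is SAP wording and one listing, plus some coding effort or a single CRF item. No new procedure or visit is needed.
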